### 3.5.2. Study Drug Discontinuation Considerations

The medical monitor should be consulted prior to study drug discontinuation when medically feasible.

Study drug must be permanently discontinued in the following instances:

- Any opportunistic infection
- Any **serious** infection that requires antimicrobial therapy or hospitalization, or any infection that meets SAE reporting criteria.
- Febrile neutropenia (temperature  $> 38.3^{\circ}\text{C}$  or a sustained temperature of  $> 38^{\circ}\text{C}$  for more than one hour) with absolute neutrophil count of  $< 1,000/\text{mm}^3$
- Symptomatic anemia (eg, signs/symptoms including pallor, shortness of breath, new heart murmur, palpitations, lethargy, fatigue ) with hemoglobin  $< 7.5$  g/dL, or if transfusion is indicated regardless of hemoglobin value
- Complicated herpes zoster infection (with multi-dermatomal, disseminated, ophthalmic, or CNS involvement)
- Evidence of active HCV during the study, as evidenced by HCV RNA positivity
- Evidence of active HBV during the study, as evidenced by HBV DNA positivity
- Any thromboembolic event that meets SAE reporting criteria
- Unacceptable toxicity, or toxicity that, in the judgment of the investigator, compromises the subject's ability to continue study-specific procedures or is considered to not be in the subject's best interest
- Subject request to discontinue for any reason
- Subject noncompliance
- Pregnancy during the study; refer to Section [7.7.2.1](#)
- Discontinuation of the study at the request of the Sponsor, a regulatory agency or an institutional review board or independent ethics committee (IRB/IEC)
- Subject use of prohibited concurrent therapy may trigger study drug discontinuation; consultation should be made with the medical monitor.

- Laboratory Criteria: After becoming aware of any of the below described abnormal laboratory changes occurring at any one time, an unscheduled visit (ie, sequential visit) should occur to retest within 3 to 7 days (except creatinine, which should be retested 7 to 14 days apart).
  - 2 sequential neutrophil counts  $< 750$  neutrophils/mm^3 (international system units [SI]:  $< 0.75 \times 10^9$  cells/L)
  - 2 sequential platelet counts  $< 75,000$  platelets/mm^3 (SI:  $< 75.0 \times 10^9$  cells/L)
  - 2 sequential aspartate aminotransferase (AST) or alanine aminotransferase (ALT)  $> 3$  times the upper limit of normal range (ULN) and at least one of the following confirmed values:

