- TB Assessment – Must have negative QuantiFERON® test (or centrally reported equivalent assay) during screening, and negative chest x- ray within 3 months of or during screening for those with no evidence or history of TB. Positive or negative results must not be repeated. An indeterminate result should be repeated once and the second result (if positive or negative) will be accepted. Two sequential indeterminate results is considered a positive result for the purpose of the study. Subjects with previously treated latent or active TB requires sponsor approval (See inclusion criterion 7 for details). Subjects who are diagnosed with latent TB at screening must initiate an adequate course of prophylaxis as per local standard of care for a minimum of 4 weeks prior to randomization. Subject may initiate study drug dosing only after consultation with the medical monitor.
- Obtain blood samples (reference Study Procedures Table [[Appendix 2](#)])
  - **HCV Screening Guidelines**
    - Subjects with positive HCV antibody at Screening require reflex testing for HCV RNA. Subjects with HCV RNA  $\geq$  lower limit of quantification (LLOQ) at Screening will be excluded. Subjects with positive HCV antibody but HCV RNA  $<$  LLOQ are eligible.
  - **HBV Screening and Surveillance Guidelines**
    - Subjects with positive HBV surface antigen (HBsAg) at Screening are excluded.
    - Subjects who are positive for HBV surface antibody (HBsAb), but negative for **both** HBsAg and HBV core antibody (HBcAb) at Screening are eligible.
    - Subjects with positive HBcAb require reflex testing for HBV DNA. Subjects with HBV DNA  $\geq$  LLOQ at Screening will be excluded. Subjects with positive HBcAb and HBV DNA  $<$  LLOQ are eligible, but will require ongoing HBV DNA monitoring every 3 months during this study. These subjects may require prophylactic treatment per investigator discretion in accordance with local guidelines/standard of care.

- In Japan and where required by local guidelines, subjects with positive HBcAb and/or positive HBsAb will require reflex testing for HBV DNA at Screening. Subjects with positive HBcAb and/or HBsAb but with HBV DNA < LLOQ at Screening are eligible for the study. These subjects will require ongoing HBV DNA monitoring every 4 weeks in accordance with local guidelines during this study.
- Any subject who has HBV DNA  $\geq$  LLOQ during the study will be discontinued (reference Section 3.5.2).

— **HIV Screening Guidelines**

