- Subjects who have HIV infection, regardless of virologic status, are excluded from the study.
- Obtain blood samples for serum pregnancy test (for females of childbearing potential only)
- Obtain stool sample (reference Study Procedures Table [Appendix 2])
  - A stool sample will be obtained for culture for pathogenic bacteria, ova and parasite evaluation, and *C. difficile* toxin assay during screening for the purposes of determining eligibility.
- Obtain urine sample (reference Study Procedures Table [Appendix 2])
- Obtain urine sample for urine drug screen (reference Study Procedures Table [Appendix 2])
- Review subject eligibility criteria (centrally calculated CDAI, PRO2 and labs), prior to performing a full video ileocolonoscopy with biopsies within 14 days prior to baseline visit: Biopsy samples will be collected and sent to central laboratory for storage and then to specialty laboratories for subsequent analysis.
  - Record local endoscopic assessment
- Baseline SES-CD scoring and calculation performed by central reader (Appendix 5).

A single retest of screening labs is permitted only if there is reason to believe the retest value will be within accepted parameters, or if the initial value was either due to a sample processing error or due to an extenuating circumstance

Subjects meeting all of the inclusion criteria and none of the exclusion criteria will return to the clinic within 30 days after screening for randomization into the study. Subjects may be randomized more than 30 days after screening if they receive permission from the medical monitor. If the subject does not begin the treatment within this 30-day window, specific screening evaluation procedures may need to be repeated at the direction of the medical monitor. No more than one repeat screening visit is allowed for each subject, unless prior written approval has been provided by the Sponsor. All screening procedures will need to be repeated during the repeat screening visit except for the ileocolonoscopy procedures. Ileocolonoscopy procedures from the previous screening attempt that fall within the specified timeframe (i.e, ileocolonoscopy with biopsies within 14 days prior to Day 1 visit) do not need to be repeated.

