### **6.4. Study Assessments**

Please refer to the Study Procedure Table in [Appendix 2](#) for all procedures and time points to be conducted after randomization.

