#### 6.4.3.1. Clinical Laboratory Evaluations

The hematology, serum chemistry, coagulation laboratory, and stool analyses will be performed at a central laboratory. Reference ranges will be supplied by the central laboratory and will be used by the investigator to assess the laboratory data for clinical significance and pathological changes.

Blood samples will be collected by venipuncture (or optional indwelling catheter for PK sampling days) in the arm at the time points indicated in the Study Procedures Table ([Appendix 2](#)). In addition, urine samples for the clinical laboratory assessments will be collected. An overnight fast (no food or drinks, except water) of at least 8 hours will be required prior to collection of blood samples for lipid testing.

A stool sample should also be collected at any time during the study for culture for pathogenic bacteria, ova and parasites, and *C. diff* toxin assay when a subject becomes symptomatic, including worsening or return of disease activity.

Refer to [Appendix 8](#) for table of clinical laboratory tests.

Laboratory values outside the normal range will be flagged and clinical relevance will be assessed by the investigator. More frequent sampling as well as additional tests may be performed as deemed necessary by the investigator.

Note that in the case where clinically significant laboratory test results are a potential reason for discontinuation from the study drug and/or withdrawal from the study, retesting of the affected parameter(s) should be prompt (within 3 to 7 days [except creatinine, which should be retested 7-14 days apart] ).

The details of sample handling and shipment instructions will be provided in a separate laboratory manual.

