Visit	1	2	3	4	5	6	7	8	9	10	11	12	13	14	15	16	17	18	19	20	PTx a	ET
Week		0	2	4	6	10	11	14	17	20	23	26	30	34	38	42	46	50	54	58		
Study Day	-30 to -1	1	15	29	43	71	78	99	120	141	162	183	211	239	267	295	323	351	379	407		
Visit Window (±)			±3	±3	±3	±2	±3	±5	±5	±5	±5	±5	±5	±5	±5	±5	±5	±5	±5	±5	±3	±3

Urine drug screen k	X																					
Urinalysis	X	X				X														X		
Pregnancy Test l	X	X		X	X	X		X	X	X	X	X	X	X	X	X	X	X	X	X	X	X
TB m	X																					
Chest x-ray n	X																					
HBV, HCV, HIV screening o	X																					
HBV DNA monitoring (Japan) p				X	X	X		X	X	X	X	X	X	X	X	X	X	X	X	X	X	
HBV DNA monitoring (other regions) p						X				X				X				X		X		
Hematology	X	X	X	X	X	X		X		X		X		X		X		X		X	X	X
Chemistry	X	X	X	X	X	X		X		X		X		X		X		X		X	X	X
Lipid profile (fasting) q		X				X						X									X	X

CCI																							
Serum immunoglobulin		X		X		X						X									X	X	X

Period	Screen	Treatment																				Follow-Up		
		2	3	4	5	6	7	8	9	10	11	12	13	14	15	16	17	18	19	20	PTx a	ET		
Visit	1																							
Week		0	2	4	6	10	11	14	17	20	23	26	30	34	38	42	46	50	54	58				
Study Day	-30 to -1	1	15	29	43	71	78	99	120	141	162	183	211	239	267	295	323	351	379	407				
Visit Window (±)			±3	±3	±3	±2	±3	±5	±5	±5	±5	±5	±5	±5	±5	±5	±5	±5	±5	±3	±3			
Blood TCR/BCR repertoire sample f		X		X		X						X								X				

PK collection (sparse) s				X		X						X									X	
-------------------------------------	--	--	--	---	--	---	--	--	--	--	--	---	--	--	--	--	--	--	--	--	---	--

[figure not shown]
PK substudy u				X																		
--------------------------	--	--	--	---	--	--	--	--	--	--	--	--	--	--	--	--	--	--	--	--	--	--

- a The Post-Treatment (PTx) visit should occur 30 days after the last dose of study drug. Only subjects who roll over into the LTE study (GS-US-419-3896) will not complete PTx assessments.
- b For subjects who terminate prior to Week 10.
- c A complete physical examination (PE) including, vital signs, body weight, and height will be performed at screening. A symptom directed PE may be done at other time points.
- d Once a subject meets all other eligibility criteria (centrally calculated CDAI, PRO2 and labs), perform the screening full video ileocolonoscopy with biopsies within 14 days prior to Day 1 visit.

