- e The investigator (ie local endoscopist) may enter endoscopic assessment data based on the SES-CD in the eCRF (Appendix 5). The locally read SES-CD score may not be used for eligibility or assessing endoscopic response for primary efficacy analysis, and it is not a substitute for the centrally read score, CCI [REDACTED]
- f The screening CDAI will be used as the Day 1 measurement. The CDAI patient reported outcomes of stool frequency and abdominal pain will be used to derive the PRO2 score.
- g CCI [REDACTED]
- h Patient global impression change (PGI-C) should be assessed at Weeks 10 and 58 only. Patient global impression of severity (PGI-S) should be assessed at Day 1, Weeks 10 and 58.
- i Subjects should begin filling out the e-Diary the day of their initial screening visit and continue to fill it out throughout the remainder of the study.
- j Stool samples should be collected to rule out infectious causes when disease worsens.
- k Positive cocaine test disqualifies subject; positive amphetamines, barbiturates, benzodiazepines, and opioids require medical monitor review.
- l All females meeting the childbearing potential criteria must have a serum pregnancy testing at screening and a urine pregnancy test must be completed in clinic every 4 weeks at a minimum. If any pregnancy test is positive, study drug should be immediately interrupted and the subject should have a serum pregnancy test in clinic.
- m Proof of no active or untreated latent TB at screening. Subjects who are diagnosed with latent TB at screening must initiate an adequate course of prophylaxis as per local standard of care for a minimum of 4 weeks prior to randomization. Subject may initiate study drug dosing only after consultation with the medical monitor.
- n Chest x-ray (views as per local guidelines) taken at screening or within the 3 months prior to screening (with the report or films available for investigator review) without evidence of active or latent TB infection
- o Hepatitis B surface Ag, surface Ab and core Ab, reflex HBV DNA, Hepatitis C Ab, reflex HCV RNA, HIV Ag/Ab, reflex HIV 1/2 Ab at Screening (Section 6.2.1).
- p In Japan, subjects with negative HBsAg, positive HBcAb and/or positive HBsAb at Screening require HBV DNA monitoring every 4 weeks in accordance with local guidelines (Section 6.2.1). In other regions, subjects with negative HBsAg and positive HBcAb require HBV DNA monitoring every 3 months in accordance with local guidelines (Section 6.2.1)

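### Outside Japan, HBV DNA testing is required every 3 months, but the visit table schedules no test for 112 days between Weeks 34 and 50

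*Protocol*

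**What the plan says.** Protocol Section 6.2.1 sets the hepatitis B rules. "Subjects with positive HBcAb require reflex testing for HBV DNA", and a subject with quantifiable HBV DNA is excluded. A subject with positive HBcAb and HBV DNA below the limit of quantification may enter, but "will require ongoing HBV DNA monitoring every 3 months during this study". For Japan the interval is 4 weeks.

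Appendix 2 repeats the rule in footnote p: "In other regions, subjects with negative HBsAg and positive HBcAb require HBV DNA monitoring every 3 months in accordance with local guidelines". The footnote is attached to the row that begins "HBV DNA monitoring (other regions", which marks Weeks 10, 20, 34, 50 and 58. SAP Appendix 1 carries the same row and the same footnote.

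Section 6.4 refers sites to the Appendix 2 table "for all procedures and time points to be conducted after randomization". Section 3.5.2 lists among the reasons for permanent discontinuation: "Evidence of active HBV during the study, as evidenced by HBV DNA positivity".

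**The concern.** The text and the table give two different schedules for one safety test. A site that follows the marks exactly, as Section 6.4 invites it to do, cannot meet the 3-month rule between Weeks 34 and 50. To comply, it must add a test that the table does not schedule.

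The test triggers a mandatory stopping rule in subjects with past hepatitis B exposure who may be taking a JAK inhibitor. If reactivation occurs early in the gap, the marked schedule detects it later than the protocol intends, and dosing continues meanwhile.

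**Working it through.** **Inputs.** The marks are those of the row for regions other than Japan (protocol Appendix 2, identical in SAP Appendix 1). The study days come from the same table: Week 10 = Day 71, Week 20 = Day 141, Week 34 = Day 239, Week 50 = Day 351, Week 58 = Day 407. The window is ±2 days at Week 10 and ±5 days at Weeks 20, 34 and 50. The documents give no maximum in days, so I take 3 months as about 91 days. Three calendar months are never more than 92.

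**Intervals between marked tests.** Interval = later study day − earlier study day. The range subtracts or adds both windows.

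| Interval | Days | With windows | Against 91 days |
|---|---|---|---|
| Week 10 to 20 | 141 − 71 = 70 | 63 to 77 | meets the rule |
| Week 20 to 34 | 239 − 141 = 98 | 88 to 108 | marginal |
| Week 34 to 50 | 351 − 239 = 112 | 102 to 122 | exceeds it by 11 to 31 |
| Week 50 to 58 | 407 − 351 = 56 | not limiting | meets the rule |

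In months, the longest gap is 112 / 30.44 = 3.68. Even its minimum of 102 days exceeds 92, so the result does not depend on how months are converted to days.

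**Screening to Week 10.** SAP Section 3.8.1.1 has no Day 0. From Day −30 to Day 71 is 30 + 71 − 1 = 100 days, or 102 with the window. From Day −1 it is 71 days. Screening on Day −21 gives 91 days and on Day −22 gives 92. With Week 10 on its nominal day, the interval is therefore late only if screening falls on Day −22 or earlier. That includes delayed randomization, which Section 6.2.1 allows: "Subjects may be randomized more than 30 days after screening if they receive permission from the medical monitor".

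**Column reading.** The marks are read from tab positions in text extracted from PDF. Three checks support the reading:
- Both copies of the row agree.
- All five marks fall on visits with hematology and chemistry.
- Shifting the row one column either way leaves only one of the five marks on such a visit.

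The adjacent Japan row, read the same way, never exceeds 28 days between marked visits, which matches its 4-week rule.

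**Who is affected.** The documents give no HBcAb prevalence, so I assume 1% to 10%. The sample-size section expects about 176 responders per filgotinib dose, so 2 × 176 = 352, of whom 3.5 to 35.2 would be HBcAb-positive. After 2:1 re-randomization about 352 × 2/3 = 235 stay on filgotinib, of whom 2.3 to 23.5 would be positive. These counts are before removing subjects in Japan and those who leave before Week 34, and before adding induction-placebo responders.

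**The case against.** The strongest counter-argument is that the correct rule is attached to the row. Footnote p is part of the table to which Section 6.4 points, it cites Section 6.2.1, and nothing permits a longer interval. A site that reads the footnote can comply by adding a test. This is true and limits the harm, but the marks still contradict the rule.

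The footnote's reference to local guidelines does not help. It follows a stated 3-month interval, and Section 6.2.1 gives the same interval without that qualifier.

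The column reading can also be questioned, because alignment does drift in places. For example, the last sparse-PK mark extracts under the post-treatment column although its footnote says Week 58. The drift found affects marks around Week 58, not those at Weeks 34 and 50.

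Other safeguards exist. Entry requires HBV DNA below the limit of quantification, chemistry including AST and ALT is drawn at Week 42, and prophylaxis is at the investigator's discretion. Section 6.4.3.1 adds: "More frequent sampling as well as additional tests may be performed as deemed necessary by the investigator". These reduce the risk, but none is a scheduled HBV DNA test.

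The objection carries most weight on the first interval. Counting from the screening test is only one reading of the rule; from first dose to Week 10 is 70 days. When randomization is delayed, the medical monitor may also direct that screening evaluations be repeated. I treat that interval as marginal.

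**Conclusion.** The inconsistency is real. Under the marked schedule, Weeks 34 to 50 is 112 days, at least 102 with the windows, against a rule of about 91. This finding rests only on the column reading, which is well supported. Weeks 20 to 34 exceeds 91 days nominally but can meet it within the windows. Screening to Week 10 is late only when screening is early.

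The consequence is limited to safety monitoring of a probably small HBcAb-positive group outside Japan; the head counts above rest on an assumed prevalence. The table should be corrected because the test drives mandatory discontinuation and the correction is cheap. No efficacy conclusion depends on it.

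**What to change.** Keep the 3-month rule and edit the row for regions other than Japan in protocol Appendix 2. Make the same edit in SAP Appendix 1 for consistency only.

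1. Add a mark at Week 42 (Day 295). This is the minimum edit: 112 days becomes 56 + 56.
2. Add a mark at Week 26 (Day 183): 98 days becomes 42 + 56.
3. Optionally, add a mark at Week 6 (Day 43) to cover early screening. Screening on Day −30 to Week 6 is 43 + 30 − 1 = 72 days, or 75 with the ±3-day window.

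With edits 1 and 2, the longest gap from Week 10 onward is 70 days, or 70 + 2 + 5 = 77 with windows. Hematology and chemistry are already drawn at Weeks 6, 26 and 42, so no visit or blood draw is added. The cost is one to three HBV DNA assays per affected subject.

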**Appendix 3. Management of Clinical and Laboratory Adverse Events**

#### Appendix 4. Crohn's Disease Activity Index (CDAI) and Patient Reported Outcomes – 2 items (PRO2)

The Crohn's Disease Activity Index (CDAI) will be calculated as follows:

Variable no.	Variable	Variable description	Multiplier
1	Liquid or very soft stool	Daily stool count is summed for 7 days	2
2	Abdominal pain	Sum of 7 days of daily ratings as 0 = none, 1 = mild, 2 = moderate, 3 = severe	5
3	General wellbeing	Sum of 7 days of daily ratings as 0 = generally well, 1 = slightly below par, 2 = poor, 3 = very poor, 4 = terrible	7
4	Complications	Number of listed complications: Arthritis or arthralgia Erythema nodosum, pyoderma gangrenosum or aphthous stomatitis Iritis or uveitis Anal fissures or fistulae or abscess Other fistula Fever over 37.8 C [100 F] during past week	20 each
5	Use of anti-diarrheal medications	Use of diphenoxylate or loperamide or other opiate for diarrhea 0 = No, 1 = Yes	30
6	Abdominal mass	0 = none, 2 = questionable, 5 = definite	10
7	Hematocrit*	Males: 47 – Hct [%] Females: 42 – Hct [%] *Result must be greater than or equal to 0. If negative result enter 0	6 × difference
8	Weight*	Percentage deviation from standard weight (1 – weight / standard weight) × 100 *Limit of -10	1
CDAI score			TOTAL

CDAI = Crohn's Disease Activity Index; Hct = hematocrit  
{Sandborn 2002}

The patient reported outcomes of liquid or very soft stool and abdominal pain (PRO2) score will be assessed as follows:

Variable no.	Variable	Variable description
1	Liquid or very soft stool	Mean of the daily (liquid or very soft) stool count for 7 days
2	Abdominal pain	Mean of 7 days of daily ratings as 0 = none, 1 = mild, 2 = moderate, 3 = severe

{Daperno 2004}

Each PRO2 score will be rounded to the nearest integer for determination of eligibility and calculation of end points.

**Appendix 5. Simple Endoscopic Score for Crohn’s Disease (SES-CD)**

Variables	Score			
	0	1	2	3
Size of ulcers (cm)	None	Aphthous ulcers (diameter 0.1-.05)	Large ulcers (diameter 0.5-2)	Very large ulcers (diameter > 2)
Ulcerated Surface (%)	None	< 10	10-30	> 30
Affected surface (%)	Unaffected segment	< 50	50-75	> 75
Presence of narrowings	None	Single, can be passed	Multiple, can be passed	Cannot be passed

\* Total SES-CD: sum of the values of the 4 variables for the 5 bowel segments. Values are given to each variable and for every examined bowel segment (eg, rectum, left colon, transverse colon, right colon, and ileum)  
 {Daperno 2004}

**Appendix 6. CTCAE Grading Scale for Severity of Adverse Events**

Please refer to the Common Terminology Criteria for Adverse Events (CTCAE) Version 4.03, which can be found at:

[http://evs.nci.nih.gov/ftp1/CTCAE/CTCAE\\_4.03\\_2010-06-14\\_QuickReference\\_8.5x11.pdf](http://evs.nci.nih.gov/ftp1/CTCAE/CTCAE_4.03_2010-06-14_QuickReference_8.5x11.pdf)

For AEs associated with laboratory abnormalities, the event should be graded on the basis of the clinical severity in the context of the underlying conditions; this may or may not be in agreement with the grading of the laboratory abnormality.

The only modification to the CTCAE criteria is the addition of a Grade 1 upper respiratory infection as follows:

CTCAE V4.0 Term	Grade 1	Grade 2	Grade 3	Grade 4	Grade 5	CTCAE V4.03 AE Term Definition
Upper respiratory infection	Mild symptoms; symptomatic relief (eg, cough suppressant, decongestant)	Moderate symptoms; oral intervention indicated (eg, antibiotic, antifungal, antiviral)	IV antibiotic, antifungal, or antiviral intervention indicated; radiologic, endoscopic, or operative intervention indicated	Life-threatening consequences; urgent intervention indicated	Death	A disorder characterized by an infectious process involving the upper respiratory tract (nose, paranasal sinuses, pharynx, larynx, or trachea).

